3.4. EXPANSION cohorts

- Once the MTD has been defined based on the dose escalation study, the expansion cohorts will be opened. All patients will be treated at the MTD of Trabectedin (as defined in the escalation trial) given in association with durvalumab with the same schedule as in the phase I trial.
- Following the expansion cohorts, the RP2D for Trabectedin will be identified by the steering committee based on safety data from patients included in the dose escalation part and the expansion cohorts, as well as PD data. Data from all patients (escalation + expansion cohorts) will be used to define the RP2D.

3.5. Patient's replacement

See section 10.2.

4. SELECTION OF PATIENTS

4.1. Inclusion Criteria

1. Histology :

- Soft-tissue sarcoma histologically confirmed. In care outside a center of the RRePS Network, a central review is necessary ([name] team),
- histologically confirmed ovarian carcinoma (carcinosarcoma included) without known g/s BRCA mutation,

2. Ovarian carcinoma must have received at least one line of platinum-containing regimen.

3. Metastatic or unresectable locally advanced disease, not amenable to curative therapy,

4. Age \geq 18 years,

5. Eastern Cooperative Oncology Group (ECOG) performance status (PS) \leq 1,

6. Life expectancy $>$ 3 months,

7. Patients must have measurable disease (lesion in previously irradiated field can be considered as measurable if progressive at inclusion according to RECIST v1.1) defined as per RECIST v1.1 with at least one lesion that can be measured in at least one dimension (longest diameter to be recorded) as \geq 10 mm with spiral CT scan,

8. Documented disease progression according to RECIST v1.1 before study entry,

9. Patient must comply with the collection of tumor biopsies,

10. At least 1 line of chemotherapy in the palliative setting, with use of anthracyclines (for STS),

11. At least three weeks since last chemotherapy, immunotherapy or any other pharmacological treatment for neoplastic disease and/or radiotherapy,

12. Adequate hematological, renal, metabolic and hepatic function:

a. Hemoglobin \geq 9 g/dl (patients may have received prior red blood cell [RBC] transfusion, if clinically indicated); absolute neutrophil count (ANC) \geq 1.5 \times 10⁹/l, and platelet count \geq 100 \times 10⁹/l.

b. Alanine aminotransferase (ALT), aspartate aminotransferase (AST) \leq 2.5 \times upper limit of normality (ULN) and alkaline phosphatase (AP) \leq 2.5 \times ULN

c. Total bilirubin \leq ULN

d. Albumin \geq 25 g/l

e. Calculated creatinine clearance (CrCl) $>$ 60 ml/min (according to Cockcroft Gault formula).

- f. Thyroid function within normal laboratory ranges (TSH, free T3, free T4)
- g. Creatine PhosphoKinase (CPK) $\leq 2.5 \times$ ULN.

13. Women of childbearing potential must have a negative serum pregnancy test within 72 hours prior to receiving the first dose of trial medication. Both women and men must agree to use a highly effective method of contraception throughout the treatment period and for six months after discontinuation of treatment. Acceptable methods of contraception are described in protocol section 7.5,

14. No prior or concurrent malignant disease diagnosed or treated in the last 2 years except for adequately treated *in situ* carcinoma of the cervix, concomitant endometrial carcinoma stage IA grade 1, basal or squamous skin cell carcinoma, or *in situ* transitional bladder cell carcinoma,

15. Recovery to grade ≤ 1 from any adverse event (AE) derived from previous treatment (excluding alopecia of any grade and non-painful peripheral neuropathy grade ≤ 2) according to the National Cancer Institute Common Terminology Criteria for Adverse Events (NCI-CTCAE, version 4.03),

16. Voluntarily signed and dated written informed consent prior to any study specific procedure,

17. Patients with a social security in compliance with the French law.

4.2. Exclusion Criteria

- 1. Previous treatment with Trabectedin or an anti-PD-1, anti-PD-L1, anti-PD-L2, including Durvalumab,
- 2. Current or prior use of immunosuppressive medication including any use of oral glucocorticoids, within 21 days before the first dose of Durvalumab, with the exceptions of intranasal and inhaled corticosteroids or systemic corticosteroids at physiological doses,
- 3. Active or prior documented inflammatory bowel disease (e.g., Crohn's disease, ulcerative colitis),
- 4. Has an active autoimmune disease requiring systemic treatment within the past 2 years (ie, with use of disease modifying agents, corticosteroids or immunosuppressive drugs). Replacement therapy (e.g., thyroxine, insulin, or physiologic corticosteroid replacement therapy for adrenal or pituitary insufficiency) is not considered a form of systemic treatment,
- 5. Has evidence of active non-infectious pneumonitis,
- 6. Has an active infection requiring systemic therapy,
- 7. Currently active bacterial or fungus infection ($>$ grade 2 NCI-CTCAE HIV1, HIV2, hepatitis A or hepatitis B or hepatitis C infections),
- 8. Known central nervous system malignancy (CNS),
- 9. Men or women of childbearing potential who are not using an effective method of contraception as previously described; women who are pregnant or breast feeding,
- 10. Previous enrolment in the present study,
- 11. Patient unable to follow and comply with the study procedures because of any geographical, social or psychological reasons,
- 12. Has received a live vaccine within 30 days prior to the first dose of trial treatment,
Note: the killed virus vaccines used for seasonal influenza vaccines for injection are allowed; however intranasal influenza vaccines (e.g., FluMist[®]) are live attenuated vaccines and are not allowed.
- 13. Known hypersensitivity to any involved study drug or any of its formulation components,
- 14. Tumors not accessible for biopsy,
- 15. Known history of active tuberculosis,
- 16. Person under judicial protection or deprived of liberty,
- 17. Cardiac dysfunction:
 - LVEF (Left Ventricular Ejection Fraction) $< 40\%$ at baseline;
 - or clinically symptomatic cardiac dysfunction (any % of LVEF at baseline).
- 18. Concomitant use of strong inhibitors or inductors of cytochrome CYP3A4 taken within 21 days prior to the first dose of study drug

STUDY PLAN

4.3. Duration of Study (Whole Population)

The total duration of the study will be approximately 36 months, including about 18 months of active enrolment.

Planned start date (first patient on study): February 2017.

Follow-up: 12 months

4.3.1. Dose escalation part

Follow-up: 6 months

End of study occurs when all of the following criteria have been satisfied:

- The trial is closed to recruitment
- AND
- All patients have disease progression or are no longer on study medication
- AND
- The last included patient has been followed for 6 months or is deceased

4.3.2. Expansion cohort

Follow-up: 12 months

End of study occurs when all of the following criteria have been satisfied:

- The trial is closed to recruitment
- AND
- All patients have disease progression or are no longer on study medication
- AND
- The last included patient has been followed for 12 months or is deceased

4.4. Definitions of duration of Study and Treatment (Per Patient)

Patients will receive study treatment as long as it is considered to be in their best interest. Patients will be evaluated at scheduled visits in up to three study periods:

- **Pre-treatment (PRE TT):** from signature of informed consent to the first administration of study drugs.
- **Treatment (TT):** from the first administration of study drugs to treatment discontinuation.
- **Follow-up (FUP):** after treatment discontinuation, patients will be followed up four weeks later for toxicities, and beyond if grade 3 or 4 toxicity, until resolution.

Patients who discontinue treatment *without progression* will be **followed every 12 weeks** until:

1. Disease progression,
2. Initiation of other antitumor therapy,
3. Death, or
4. The date of study termination, whichever occurs first.

After documented progression or start of a new antitumor therapy, patients will be **followed every 6 months until:**

1. Death, or
2. The date of study termination, whichever occurs first.

Patients will be considered to be **on-study** from the signature of the informed consent to the end of follow-up period.

Patients will be considered to be **on-treatment** for the duration of their treatment until 30 days (4 weeks) after the last treatment administration, except if the patient starts a new antitumor therapy before this period.

Patients may withdraw their consent at any time; no further study activities will be conducted on them.

Treatment discontinuation occurs when an enrolled patient ceases to receive the study medication or starts a new antitumor therapy, regardless of the circumstances, and is defined as 30 days after the day of the last treatment administration, unless the patient starts a new antitumor therapy, in which case the date of administration of this new antitumor therapy will be considered the date of treatment discontinuation. The primary reason for any discontinuation will be recorded on the patient's case report form (CRF). If a patient discontinues treatment, every effort should be made to complete the scheduled assessments. Administration of the study treatments should be permanently discontinued if this is considered to be in the best interest of the patient. More specifically, treatment will be discontinued due to any of the following reasons:

- Withdrawal of consent or lost to follow-up,
- Disease progression,
- Adverse event that, in the opinion of the investigator or the sponsor, contraindicates further dosing,
- Subject is determined to have met one or more of the exclusion criteria for study participation at study entry and continuing investigational therapy might constitute a safety risk,
- Pregnancy or intent to become pregnant,
- Grade ≥ 3 infusion reaction,
- Initiation of alternative anticancer therapy including another investigational agent,
- Intercurrent illness of sufficient magnitude to preclude safe continuation of the study,
- Patient refusal and/or non compliance with study requirements,
- Protocol deviation with an effect on the risk/benefit ratio of the clinical trial

Patients still experiencing a non-progression after 6 cycles will then be able to continue treatment off-study at the discretion of the investigator.

Study discontinuation occurs when an enrolled patient ceases to participate in the study, regardless of the reason (as detailed under "Follow-up" in Section 3.2.8). Patients have the right to withdraw consent at any time; if this is the case, no further follow-up should be performed.

The date and reason for study discontinuation will be clearly documented on the patient's CRF.

4.5. PROTOCOL DEVIATION

A protocol deviation is defined as any departure from what is described in the protocol of a clinical trial approved by an Independent Ethics Committee/Institutional Review Board (IEC/IRB) and Competent Authorities. Therefore, this applies to deviations related to patient inclusion and clinical procedures (e.g., assessments to be conducted or parameters to be determined), and also to other procedures described in the protocol that concern the Good Clinical Practice (GCP) guidelines or ethical issues (e.g., issues related to obtaining the patients' Informed Consent, data reporting, the responsibilities of the investigator, etc.).

Deviations with no effects on the risk/benefit ratio of the clinical trial (such as minimal delays in assessments or visits) will be distinguished from those that might have an effect on this risk/benefit ratio, such as:

- Deviations that might affect the clinical trial objectives, such as those involving the inclusion/exclusion criteria (which could mean that the patient is not eligible for the trial) and those having an effect on patient evaluability.
- Deviations that might affect the patient's well-being and/or safety, such as an incorrect dosing of the investigational medicinal product due to not following dose adjustment specifications or an incorrect preparation of the medication.
- Deviations related to the following of GCP guidelines as described in the protocol and regulations in force, such as deviations when obtaining the Informed Consent or not following the terms established for reporting serious adverse events (SAEs), etc.

The investigators may suggest to the Sponsor the authorization of certain protocol deviations, especially if they are related to the inclusion/exclusion criteria or if they may have an effect on the evaliability of the patients. As a general rule, NO deviations that may have an effect on the risk/benefit ratio of the clinical trial will be authorized. Protocol deviations considered particularly relevant, which are related to ethical issues, fulfillment of GCP guidelines and trial procedures, will be notified to the pertinent IEC/IRB and, if pertinent, to the relevant authorities as established by local regulations.

4.6. SCREENING EVALUATION

During the pre-treatment period, and once the patient has signed the informed consent form, the Investigator will confirm the patient's eligibility for the study by conducting the assessments detailed below.

Screening assessments.

	ASSESSMENT	TIME
1. History and clinical examination	♦ Signed by the patient/legal representative Informed Consent Form	Prior to any specific study procedures
	♦ Medical history and baseline condition ♦ Complete physical examination ♦ Performance status (ECOG PS; see Appendix 1) ♦ Assessment of baseline signs and symptoms ♦ Concomitant treatments	Within two weeks prior to Day 1 of cycle 1 (+1 week tolerance) D-14 to D-1
	♦ Vital signs: heart rate, blood pressure, body temperature, weight and height	Within 7 days prior to Day 1 of cycle 1 (+3 day tolerance) D-7 to D-1
	♦ Demographic data ♦ Primary diagnostic and prior treatment/s data: • Date of diagnosis of the primary disease • Prior treatments (surgery, radiotherapy, chemotherapy, immunotherapy), specifying the date of best response and the time to progression	Within four weeks prior to Day 1 of cycle 1 D-28 to D-1
2. Pathology	♦ Central review to confirm soft-tissue sarcoma diagnosis, except in case of diagnosis confirmed by the RRePS Network ♦ Histologically confirmed ovarian carcinomas	Material sent within 7 days after signed informed consent
3. Laboratory tests	♦ Hematology: neutrophils, lymphocytes, basophils, eosinophils, monocytes, haemoglobin, haematocrit, platelet count, red blood cell count, total white cell count, VGM, CCMH, TCMH. ♦ Biochemistry: Serum electrolytes (Na ⁺ , K ⁺ , Cl ⁻ , Mg ⁺⁺ and Ca ⁺⁺), liver function tests (AST, ALT, total bilirubin ⁺ , GGT and AP), LDH, creatinine, glucose, CPK, total proteins, urea, creatinine clearance albumin, lipase, amylase, bicarbonates, uric acid. ♦ Thyroid function: TSH, T3 and T4 ♦ CA 125 for ovarian carcinoma only ♦ Coagulation: aPTT, INR ♦ Serology: Hepatitis A antibody, Hepatitis B surface antigen, Hepatitis C antibody, and HIV antibody ♦ Urinalysis: bilirubin, blood, glucose, ketones, pH, protein, specific gravity, colour and appearance	Within 7 days prior to inclusion (+3 days tolerance). D-7 to D-1

	ASSESSMENT	TIME
4. Creatinine clearance	• Calculated using the Cockcroft formula (see Appendix 2)	Within 7 days prior to inclusion (+3 days tolerance) D-7 to D-1
5. Pregnancy test, if applicable	Measurement of serum human chorionic gonadotropin (HCG)	Within 7 days prior to Day 1 of cycle 1 (+1 day tolerance) D-7 to D-1
6. Tumor assessment	• CT-scan or MRI of all measurable sites, as per RECIST 1.1 (Appendix 3)	Within four weeks prior to Day 1 of cycle 1 (+1 week tolerance) D-28 to D-1
7. Other tests	• Intercurrent events, concomitant diseases and treatments.	Within two weeks prior to Day 1 of cycle 1. D-14 to D-1
8. LVEF	• Echocardiography	Within 14 days prior to Day 1 of cycle 1 (+1 day tolerance) D-14 to D-1

ALT, alanine aminotransferase; AP, alkaline phosphatase; aPTT, activated partial thromboplastin time; AST, aspartate aminotransferase; CCMH: Mean corpuscular hemoglobin concentration ; CPK, creatine phosphokinase; ECOG PS, Eastern Cooperative Oncology Group Performance Status; GGT: gamma-glutamyltransferase ; INR: international normalized ratio; LDH, lactate dehydrogenase; MRI, magnetic resonance imaging; RECIST v1.1, Response Evaluation Criteria In Solid Tumors; TCMH: mean corpuscular haemoglobin; TSH, thyroid stimulating hormone; VGM, Mean corpuscular volume.

(†):If Total bilirubin is $\geq 2 \times \text{ULN}$ (and no evidence of Gilbert's syndrome) then fractionate into direct and indirect bilirubin

4.7. EVALUATIONS DURING TREATMENT

The following assessments will be done while the patient is on treatment.

Evaluations during treatment.

	ASSESSMENT	TIME
1. Clinical examination	• Complete physical examination	Day 1 of cycle 1
	• Performance status (ECOG PS; see Appendix 1)	Repeat on Day 8 of Cycle 1
	• Vital signs: heart rate, blood pressure, body temperature and weight	Repeat on Day 1 of each subsequent cycle
	• Assessment of signs and symptoms	Throughout the treatment period
	• Concomitant diseases and treatments	Throughout the treatment period
2. Laboratory tests*	• Hematology: neutrophils, lymphocytes, basophils, eosinophils, monocytes, haemoglobin, haematocrit, platelet count, red blood cell count, total white cell count, VGM, CCMH, TCMH.	Within 24 hours before Day 1 of cycle 1 (except coagulation)
	• Biochemistry: Serum electrolytes (Na^+ , K^+ , Cl^- , Mg^{++} and Ca^{++}), liver function tests (AST, ALT, total bilirubin [†] , GGT and AP), LDH, creatinine, glucose, CPK, total proteins, urea, albumin, bicarbonates, uric acide. Lipase and amylase (*).	Repeat on Days 8 and 15 of Cycle 1* Repeat on Days 1, 8 and 15 of Cycle 2* Repeat on Days 1 and 8 of Cycle 3* Repeat on Day 1 of each subsequent cycle*
	• Coagulation: aPTT and INR if clinically indicated	(*): at day 1 of each cycle only
	• Urinalysis (*): bilirubin, blood, glucose, ketones, pH, protein, specific gravity, colour and appearance	
	• Thyroid function: TSH. If TSH is abnormal, free T3 and free T4	Within 24 hours before Day 1 of cycle 1 Repeat on day 1 of cycle 2* Repeat on day 1 of subsequent cycles (ie. C3, C6, C9, etc.)*

	ASSESSMENT	TIME
	♦ CA 125 for ovarian carcinoma only	Repeat on day 1 Cycle 3 and every 3 subsequent cycle*
3. Creatinine clearance	♦ Calculated using the Cockcroft formula (see Appendix 2)	Within 24 hours before Day 1 of cycle 1 Repeat on Days 8 and 15 of Cycle 1* Repeat on Days 8 and 15 of Cycle 2* Repeat on Days 8 of Cycle 3* Repeat on Day 1 of each subsequent cycle*
4. Pregnancy test, if applicable	♦ Measurement of human chorionic gonadotropin (HCG)	Within 72 hours prior to Day 1 of cycle 1 (serum) Will be repeated on day 1 of each cycle, in women with childbearing potential (urine)
5. Tumor assessment	♦ CT-scan or MRI of all measurable sites, as per RECIST (see Appendix 3)	Tumor assessment must be repeated every six weeks (± 7 days) and at least four weeks after first documentation of objective response even if there are treatment delays
6. PD study – immunological biomarkers	♦ Blood samples : 1 EDTA x 4ml ; 1 EDTA x6 ml and 1 heparin x 6 ml	At cycle 1 day 1 and at cycle 2 day 1 For more details; see section 15.1.1
7. Circulating DNA	♦ Blood samples : 2 EDTA x 10 ml	At D1 of each cycle, until progression
8. Biopsy	♦ Tumor biopsy	At baseline and at cycle 2 day 8 (± 2 days) For more details; see section 15.1.1
9. Adverse events	As per NCI-CTCAE, v4.03.	Throughout the treatment period
10. LVEF	Echocardiography	Every 2-3 months throughout the treatment period

*For all laboratory tests a window of 72 hours will be allowed.

AE, adverse event; ALT, alanine aminotransferase; AP, alkaline phosphatase; aPTT, activated partial thromboplastin time; AST, aspartate aminotransferase; CCMH: Mean corpuscular hemoglobin concentration; ECOG PS, Eastern Cooperative Oncology Group Performance Status; GGT: gamma-glutamyltransferase; INR, international normalized ratio; LDH, lactate dehydrogenase; MRI, magnetic resonance imaging; NCI-CTCAE, National Cancer Institute Common Terminology Criteria for Adverse Events; PD: pharmacodynamics assessment; RECIST, Response Evaluation Criteria In Solid Tumors TCMH: mean corpuscular haemoglobin; VGM, Mean corpuscular volume.

(+): If Total bilirubin is $\geq 2 \times \text{ULN}$ (and no evidence of Gilbert's syndrome) then fractionate into direct and indirect bilirubin

4.8. EVALUATION AT the END OF TREATMENT

The end-of-treatment visit will be scheduled 30 days (4 weeks) after the last treatment administration (a window of ± 1 week is allowed).

Regardless of the reason for discontinuation, the complete workup has to be done at the end-of-treatment visit. This will include the following assessments:

- Assessment of signs and symptoms.
- Complete physical examination.
- ECOG performance status.
- Vital signs [heart rate, blood pressure, weight and temperature].
- Hematology.
- Biochemistry.
- Urinalysis
- Calculated CrCl.
- Thyroid function

- CA 125 measurement
- Clinical and radiological tumor assessment (CT-scan/MRI) (except for patients with confirmed PD at discontinuation or who had started a new treatment).
- Intercurrent events and concomitant disease and treatments.
- Safety assessment (AEs).

Adverse events must be reported for 30 days after the last treatment administration or until the start of a new antitumor therapy, whichever occurs first. All SAEs occurring within 90 days of the last treatment administration or until the start of a new antitumor therapy, whichever occurs first, will be reported. Beyond this period of time, only those SAEs suspected to be treatment-related will be reported (see Section 11).

4.9. FOLLOW-UP AFTER the END-OF-TREATMENT VISIT

- The date and reason of the study discontinuation will be recorded on the patient's CRF (see Section 5.2).
- After treatment discontinuation, patients will be followed for four weeks after until resolution of toxicities, if any.
- Patients who discontinue treatment without PD will be followed every 12 weeks until disease progression, other antitumor therapy or death or until the date of study termination, whichever occurs first.
- After disease progression, patients will be followed every 6 months until death or until the date of study termination, whichever occurs first.
- Patients who withdraw consent will not be followed with any study procedures.

All AEs (including SAEs) suspected to be treatment-related (trabectedin and/or durvalumab) or research-related will be followed-up until the events or their sequelae resolve or stabilize at a level acceptable to the Investigator and the Sponsor.

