8.2. Secondary endpoints

Phase I / Dose escalation part

- Preliminary signs of antitumor activity in terms of:
 - Best overall response is defined as the best response recorded from the start of the study treatment until the end of treatment taking into account any requirement for confirmation as per RECIST v1.1 criteria ([appendix 3](#)):
Following RECIST v1.1 recommendations:
 - The best overall response is determined once all the data for the patient is known.
 - Claimed responses will have to be confirmed at least 4 weeks later to ensure responses identified are not the result of measurement errors.
 - Objective response rate (ORR) is defined as the proportion of patients with complete response or partial response according to RECIST v1.1 criteria ([appendix 3](#)). ORR under treatment and 6-month ORR will be reported. ORR under treatment is recorded from study treatment initiation until the end of treatment. Following RECIST v1.1 recommendations:
 - ORR under treatment is determined once all the data for the patient is known.
 - Claimed responses will have to be confirmed at least 4 weeks later to ensure responses identified are not the result of measurement errors.
 - Progression-free rate (PFR) is defined as the proportion of patients with complete response, partial response or stable disease more than 24 weeks as defined as per RECIST v1.1 criteria ([appendix 3](#)). 6-month PFR will be reported. . Following RECIST v1.1 recommendations, claimed responses will have to be confirmed at least 4 weeks later to ensure responses identified are not the result of measurement errors.
 - Progression-free survival (PFS) is defined as the time from study treatment initiation to the first occurrence of disease progression or death (of any cause), whichever occurs first. 1-year PFS rate will be reported.
 - Overall Survival (OS) is defined as the time from study treatment initiation to death (of any cause). 1-year OS rate will be reported.
- Pharmacodynamic study:
 - Blood samples:
 - Serum level of cytokines, kynurenine and immunophenotyping of circulating immune cells
 - Analyses of circulating DNA for identification and monitoring of mutations observed at the level of the circulating tumor cells (liquid biopsies concept).
 - Tumor samples: Fresh pre-treatment and on-treatment tumor biopsies will be performed. Samples will be formalin fixed and paraffin-embedded or fresh frozen, and will be analyzed for:
 - Hematoxylin and eosin staining (H&E).

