1 and 2-year Progression-Free Survival (PFS) defined as the time from study treatment initiation to the first occurrence of disease progression or death (of any cause), whichever occurs first.	
END OF TREATMENT FORM DT_SOT (Date of start of treatment) EOTSTATU (Status) EOTREAO (Reason end) DT_PROG (Date of progression if occurred) Type of progression (if progression occurred) FOLLOW UP FORM DT_FUP (date of visit) STATUSP (Vital status) PRO_LAS, DT_FPROG (date of progression) END OF STUDY (END_STU) DT_EOS (date of end of study) REA_STUD (reason) DT_DEATH (date of death)
	
Check if everything is filled in If (DT_PROG is blank) then Do; If (PRO_LAS=0) then { PFS= DT_EOS-DT_SOT ; If (REA_STUD='death') then IND_PFS=1 Else IND_PFS=0 } Else { PFS=DT_FPROG – DT_SOT; IND_PFS=1} End; Else { PFS= DT_PROG – DT_SOT; IND_PFS=1}

1 year Overall Survival (OS), OS is defined as the time from study treatment initiation to death (of any cause).	
END OF TREATMENT (EOTF) DT_SOT (start date of treatment) EOTSTAU (Status) EOTREAO (Reason end) FOLLOW UP FORM DT_FUP (date of visit) STATUSP (Vital status) END OF STUDY (END_STU) DT_EOS (date of end of study) REA_STUD (reason) DT_DEATH (date of death) DT_LFUP (date of last follow_up)
	
Check if everything is filled in If (STATUSP NE 'dead') then do; if (REA_STUD ='death') then { OS= DT_DEATH-DT_SOT; IND_OS=1; } Else {OS= DT_EOS-DT_SOT; IND_OS=0; } end; Else { OS= DT_LFUP -DT_SOT; IND_OS=1; }

Pharmacodynamic (PD) and predictive biomarkers analysis (levels of angiogenic and immunologic biomarkers in blood at baseline and different study time points).	
LABORATORY TEST BIOMARKERS AND CIRCULATING DNA
	

4 Annexes

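### Protocol sections 4.4 and 4.9 disagree on whether 6-monthly survival follow-up covers patients who start another antitumor therapy without progression, which leaves an avoidable gap in the 1-year OS data

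*Protocol*

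**What the plan says.** **Protocol 4.9 (follow-up after the end-of-treatment visit).** The first schedule reads: "Patients who discontinue treatment without PD will be followed every 12 weeks until disease progression, other antitumor therapy or death", or until study termination. The second reads: "After disease progression, patients will be followed every 6 months until death or until the date of study termination, whichever occurs first". Starting a new therapy closes the first schedule and does not open the second.

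**Protocol 4.4 (duration of study and treatment per patient).** The 12-weekly schedule has the same end points. The 6-monthly schedule has a wider trigger: "After documented progression or start of a new antitumor therapy". It then runs until death or study termination.

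**The path is foreseen.** Among the reasons for stopping treatment, 4.4 lists, separately from progression: "Initiation of alternative anticancer therapy including another investigational agent".

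**Endpoint and analysis.** Protocol 8.2 states: "Overall Survival (OS) is defined as the time from study treatment initiation to death (of any cause). 1-year OS rate will be reported". New therapy is neither an event nor a reason to censor. SAP 3.2.2 uses Kaplan-Meier. In SAP 3.2.4, a patient not recorded as dead falls to this line: "Else {OS= DT_EOS-DT_SOT; IND_OS=0". DT_EOS is labelled only as the date of end of study.

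**The concern.** OS needs vital status for every treated patient, whatever treatment follows. Under 4.9 read alone, a patient who stops study treatment without progression and then starts another therapy belongs to neither schedule. Neither document says which section prevails, and 4.9 is the section whose title covers this period, so a site could reasonably work from it.

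The SAP does not close the gap. It has no rule for new therapy and does not censor living patients at the date last known alive. Two outcomes are then possible. If the end-of-study date is entered when contact ends, the patient is censored around the switch, and Kaplan-Meier is biased if switchers have a different prognosis. If the date is study termination and nobody has asked about the patient, a missed death is counted as survival. What is at stake is the 1-year OS estimate in small cohorts, where one patient in 14 is about 7% of the sample.

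**Working it through.** **1. The two sections side by side, for a patient without progression who starts another therapy**

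| | 4.4 | 4.9 |
|---|---|---|
| 12-weekly follow-up | ends | ends |
| 6-monthly follow-up opens at | progression or new therapy | progression only |
| Next scheduled contact | within 6 months | none stated |

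Later progression would open the 6-monthly schedule under 4.9, but no visit is scheduled that would detect it.

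**2. Is there a planned figure to reproduce?** No. The plan gives no precision, rate or sample size for OS. The 14 assessable patients per cohort come from the response rule.

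**3. Size under assumed inputs.** From the plan: n = 14. Assumed: 1-year OS 60%, exponential survival, a fraction f = 0.10 or 0.20 (1.4 or 2.8 patients) who switch without progression at month 4 if alive, and a hazard ratio HR of 0.5, 1 or 2 for them against the others.

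- The others' monthly hazard h solves f·exp(−12·HR·h) + (1−f)·exp(−12h) = 0.60.
- Alive at month 4: S4 = f·exp(−4·HR·h) + (1−f)·exp(−4h).
- Share of those alive who switch: g = f·exp(−4·HR·h)/S4.
- Survival from month 4 to 12: So = exp(−8h) for the others, Ss = exp(−8·HR·h) for switchers.
- Error if censored at the switch: S4·g·(So − Ss).
- Error if counted as alive: S4·g·(1 − Ss).

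| f | HR | S4 | g | So | Ss | Censored at switch | Counted as alive |
|---|---|---|---|---|---|---|---|
| 0.10 | 0.5 | 0.843 | 0.108 | 0.697 | 0.835 | 0.587 (−1.3) | 0.615 (+1.5) |
| 0.10 | 1 | 0.843 | 0.100 | 0.711 | 0.711 | 0.600 (0) | 0.624 (+2.4) |
| 0.10 | 2 | 0.842 | 0.087 | 0.730 | 0.533 | 0.614 (+1.4) | 0.634 (+3.4) |
| 0.20 | 0.5 | 0.842 | 0.216 | 0.681 | 0.826 | 0.574 (−2.6) | 0.632 (+3.2) |
| 0.20 | 1 | 0.843 | 0.200 | 0.711 | 0.711 | 0.600 (0) | 0.649 (+4.9) |
| 0.20 | 2 | 0.841 | 0.178 | 0.747 | 0.558 | 0.628 (+2.8) | 0.666 (+6.6) |

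Brackets give the error in points against 60%. For the last row: 0.841 × 0.178 × (0.747 − 0.558) = 0.028, and 0.841 × 0.178 × (1 − 0.558) = 0.066.

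A simulation of early censoring (6,000 replicates, n = 14) agrees: 0.589, 0.598, 0.615 for f = 0.10 and 0.574, 0.600, 0.626 for f = 0.20, with a standard deviation of up to 0.146. With full follow-up the standard error is √(0.60 × 0.40/14) = 0.131.

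**4. Wider assumptions.** Take S4 = 0.85, So = 0.60, Ss from 0.30 to 0.90, and 1, 2 or 3 of 12 at-risk patients switching. Early censoring then gives errors of up to ±2.1, ±4.2 or ±6.4 points (largest: 0.85 × 3/12 × 0.30 = 0.064).

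**5. One concrete cohort.** Of 14 patients, 2 die early, 2 of the remaining 12 switch, and 5 of the other 10 die by one year. With the switchers censored, Kaplan-Meier gives 12/14 × 5/10 = 0.429. Full follow-up would give between 5/14 = 0.357 and 7/14 = 0.500. Counting both as alive reports 0.500 whatever happened to them.

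**The case against.** The strongest reply is that 4.9 is an incomplete restatement of a rule that 4.4 gives in full. It nowhere says that survival follow-up ends, and a site can satisfy both sections by applying 4.4. That stands: the gap opens only where 4.9 is used alone.

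Four stronger readings are tempting, and the documents do not support them.

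- **That 4.9 drops everyone who leaves treatment without progression.** It follows them every 12 weeks. Only those who also start another therapy before progression are affected.
- **That 4.9 ends all contact.** It still requires treatment-related adverse events to be followed until they resolve or stabilize, and protocol 10.8 keeps a patient in the study after definitive interruption. Neither schedules a vital-status check, so the OS gap remains.
- **That the SAP censors at the start of the new therapy.** Nothing sets DT_EOS to that date. Section 4.4 treats stopping treatment and leaving the study as separate events and keeps patients on study to the end of follow-up. Early censoring is one possible outcome, and missed deaths counted as alive is the other.
- **That 1-year OS is therefore biased.** With early censoring the error is zero if switchers have the same prognosis. With 4.4 followed, the gap does not arise.

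It is also fair that every rate in the illustration is assumed, that the shifts lie within one standard error, and that OS carries no decision rule. These points limit the importance of the inconsistency but do not remove it.

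**Conclusion.** The inconsistency is real and concerns a path the protocol itself anticipates. Its effect on 1-year OS is conditional: some patients must switch without progression, their site must work from 4.9 alone, and the end-of-study date then decides whether they are censored early or counted as alive. Direction and size cannot be determined from the documents. Under the main assumptions (60% 1-year OS, 10–20% switching at month 4, hazard ratio 0.5 to 2), early censoring shifts the estimate by about 1 to 3 points either way, and counting as alive shifts it up by 1.5 to 6.6 points. The standard error is about 13 points. The wider assumptions take early censoring to 6.4 points.

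OS is a secondary endpoint reported descriptively. The DLT, MTD and ORR conclusions do not depend on it. This is a low-cost consistency correction, worth making because vital status that is not collected at the time may not be recoverable.

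**What to change.** 1. **Protocol 4.9.** Replace the progression-only trigger that opens the 6-monthly sentence with the wording of 4.4, "After documented progression or start of a new antitumor therapy", and leave the rest of the sentence unchanged.
2. **SAP 3.2.4, OS program.** Censor patients not known to have died at the date last known alive instead of DT_EOS, and state that starting a new therapy does not censor OS. The program's variable list already includes follow-up visit and last-follow-up dates.

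The cost is one sentence in 4.9, a small change to the OS program, and a 6-monthly contact for a few patients that 4.4 already requires. No treatment, dose or stopping rule changes.
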